22 JUL 2024

continue for 16 hours  $\pm$  1 hour overnight. The 16-hour sputum sampling for each of the sampling days must be finished prior to the administration of the next morning's IMP. Collection will be paused for 30 minutes after evening RES301 dose where applicable.

- J: Spot or Overnight Sputum: For eligibility assessments.
- K: Blood collection for Haematology, Chemistry, and urinalysis on day 1 must be done prior to first dose.
- L:  $\beta$ -HCG Serum Pregnancy Test: All female participants.
- M: Follow-up visit: a window of  $\pm$ 3 days allowed.
- N: EBA unit inpatient: discharge

## **4.8 Data Collection and Integration**

The sampled observational information from study procedures will be recorded in the study source documents. This information will then be captured electronically onto a Clinical Study Database that is developed based on the electronic Case Report Forms (eCRFs). The variables names, types, formats, domains/tables will be based on the annotated eCRFs. Annotation of the eCRFs will be done according to the Clinical Data Interchange Standards Consortium (CDISC) study data tabulation model (SDTM) guidelines. These guidelines will ensure compliance with regulatory bodies and ensure that the FAIR principle applies to the clinical study data. The Clinical Study Database will be developed in a Clinical Data Management System (CDMS) compliant with the Protection of Personal Information Act, 2013, 21 Code of Federal Regulation (CFR) Part 11 and General Data Protection Regulation (GDPR). Laboratory results from the Safety, Mycobacteriology, and Pharmacokinetic laboratories will be imported into the Clinical Study Database and reconciled with blood and sputum sampling information. The study Data Management Plan describes the data collection and integration described in more elaborate detail.

## **4.9 Stopping Rules**

If the Investigator, the Sponsor, or Sponsor's Designee, or appropriate regulatory officials discover conditions arising during the study that indicate that the study should be halted or that the study centre should be terminated, this action may be taken after appropriate consultation among the Sponsor and Investigator/s. Conditions that may warrant termination of the study or discontinuation of a study site include, but are not limited to, the following:

- The discovery of an unexpected, serious, or unacceptable risk to the participants enrolled in the study
- A decision on the part of the Sponsor to suspend or discontinue testing, evaluation, or development of the product
- Failure of the Investigator to enroll patients into the study at a rate commensurate with good clinical research practice and acceptable to the Sponsor
- Failure of the Investigator to comply with pertinent regulations of appropriate regulatory authorities
- Submission of knowingly false information from the research facility to the Sponsor, Study Monitor, or appropriate regulatory authority
- Insufficient adherence to protocol requirements

The Regulatory Authorities and Ethics Committees/Institutional Review Boards (EC/IRB) will be informed should the study be terminated. All study materials (except documentation that must remain stored at the site) will be returned to the Sponsor. The Investigator will retain all other documents until notification is given by the Sponsor for destruction.

[figure not shown]
[figure not shown]
[figure not shown]
[figure not shown]
[figure not shown]
[figure not shown]
Participants currently on IMP will receive an appropriate TB regimen and all participants will be referred as soon as possible to the national TB programme.

## 5 Endpoints

### 5.1 Primary Endpoints

The following are the primary endpoints:

[figure not shown]
The EBATT0-14 in the Mycobacteria Growth Indicator Tube (BactecTM MGITTM 960) system as determined by the predicted rate of change in the TTP in sputum over the period day 0 to 14 will be analysed

### 5.2 Secondary Endpoints

EBA

The EBACFU (0-14) as determined by the predicted rate of change in log10CFU per ml sputum over the period day 0 to day 14 will be described

Safety and Tolerability

All adverse events will be coded using the Medical Dictionary for Regulatory Activities (MedDRA) and will be presented by preferred term within each MedDRA System Organ Class (SOC). Treatment-emergent adverse events (TEAEs) are defined as AEs which started at or after the first administration of IMP and includes those events which started prior to the first administration of IMP but which worsened after the first intake. Adverse events starting after

RESP30X-EBA: Statistical Analysis Plan22 JUL 2024

the first administration of IMP until the last scheduled visit/ assessment/ measurement will be regarded as treatment-emergent.

The incidence of the following events will be summarized by treatment:

- Incidence of treatment-emergent adverse events (TEAEs);
- Incidence of TEAEs by Severity;
- Incidence of drug-related TEAEs;
- Incidence of Serious TEAEs;
- Incidence of TEAEs leading to early withdrawal;
- Incidence of TEAEs leading to death.

Descriptive summary statistics will be presented for other safety variables: laboratory parameters, physical examination, vital signs, concomitant medication. Information on all adverse events will be collected and captured in the eCRF.

Please refer to the Section 10.1 and 10.2 for additional information regarding analyses of these endpoints.

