Coagulation Blood Screen	X																				
HIV Test and CD4 Count	X																				
Urine Drug Screen	X																				
β-HCG Serum Pregnancy Test ^O	X																				X

EBA: Early bactericidal activity, EWD: Early withdrawal, FEV1: Forced Expiratory Volume in the first second, FU: Follow-up; IMP: Investigational Medicinal Product

- A: Follow-up visit: a window of ± 3 days allowed.
- B: Physical examinations: Full will be complete at screening and targeted (symptom-directed) thereafter.
- C: Vital signs, safety laboratory: on days where there is IMP dosing, to be performed pre-dose.
- D: IMP administration: The HRZE is to be administered fasted (1 hour before, or 2 hours after food) with approximately 240 mL of water. For study purpose this food should be breakfast. Patient identification is part of the IMP administration process. Experimental arms will not receive IMP on Day 15, only control arm will receive HRZE.
- E: Concomitant Medication: collected from 14 days prior to first dose of IMP.
- F: Adverse Events: Collected from first dose of IMP to Follow-Up visit.
- G: Eligibility Assessment: Continuous from screening to just prior to first IMP dose.
- H: EBA unit inpatient: admission, anytime from initial screening to day -2, whichever is in the participant's best interest.
- I: EBA unit inpatient: discharge.
- J: Randomisation: May occur any time after eligibility has been confirmed to just prior to first IMP dose.
- K: Spot or Overnight Sputum: A screening and the last positive sputum sample (if >7 days after treatment start) on *M.tb* culture will be retained by the mycobacteriology laboratory for possible future testing. These samples contain the mycobacterium genetic material only, no participant genetic material is retained.
- L: Spot or Overnight Sputum: For eligibility assessments.
- M: Overnight sputum: Collection will start in the afternoons at approximately 15h00 and continue for 16 hours ± 1 hour overnight. The 16-hour sputum sampling for each of the sampling days must be finished prior to the administration of the next morning's IMP. Collection will be paused for 1 hour after any RESP301 dose that overlaps with the overnight sample collection window where applicable. If sputum collection is paused, participants to drink a cup of water before restarting (section 5.3.2).

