7.2. Reporting

Adverse Event (AE)

Adverse events will be collected by the investigator from the time a participant receives his/her first dose of IMP through to the final Follow up Visit. Any medical event that occurs before the first dose of IMP that is clinically significant is to be recorded as medical history, with not clinically significant events noted in the participant source documents.

Any AE (serious or non-serious) observed by the investigator or reported by the participant will be recorded on the corresponding pages of the eCRF and in the participant's medical record. The investigator will review each AE and assess its relationship to drug treatment based on all available information at the time of the completion of the case report form.

The following information will be recorded for each adverse event reported:

- diagnosis of the AE, if possible. In the case where an overall diagnosis cannot be made, each specific sign and/or symptom will be recorded as individual AEs
- date of onset
- stop date (duration) if applicable
- severity
- action taken with IMP
- other action taken

- outcome
- relationship to IMP
- occurrence
- seriousness.

Serious Adverse Events (SAE)

SAE reporting begins from the time a participant enters screening through to the final visit.

Initial Reporting

- Must be communicated by the investigator to the sponsor, study monitor and medical monitor within 24 hours of the site first being aware of the SAE, whether or not the serious event is deemed associated with the use of the drug.
- In addition, the investigator will provide a detailed SAE report form including estimates of the attribution/causality and the seriousness of the AE to the sponsor, study monitor and medical monitor and regulatory team within 24 hours of becoming aware of the SAE. The investigator will be requested to supply as much detailed information regarding the event that is available at the time of the initial contact (such as examinations carried out and laboratory results).

**ANY SERIOUS ADVERSE EVENT MUST BE REPORTED IMMEDIATELY (WITHIN 24 HOURS) TO TASK AT
THE FOLLOWING EMAIL ADDRESS: [contact]**

Follow-up Reporting

The Investigator is required to submit follow-up reports to sponsor, study monitor and medical monitor within 24 hours of becoming aware of additional information.

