## 7 General Principles

The SAP will be finalised and signed-off prior to database lock. Post-hoc analysis (analyses performed that are different from those described in the final version of the SAP) will be documented in the final CSR as changes to planned analysis. For the Demography, Safety and Tolerability, and EBA analyses, there will be two analysis periods, an interim analysis and an analysis at the end of stage 2 of the study.

All data collected will be listed, and sorted by treatment, participant number, visit, and time.

Descriptive summaries will be presented using summary statistics (e.g. number (n), mean, standard deviations (SD), median, first quartile (Q1), third quartile (Q3), minimum (min), maximum (max)) for continuous variables or number and percentage n (%) for categorical/discrete variables. Continuous variables will be expressed as median with interquartile range for skewed data and mean with SD for normal data. The percentages will not be provided for a zero count. The mean, median, SD, Q1, and Q3 will be presented to 1 more decimal place (dp) than the raw data, and min and max to the same number of dps as the raw data. Percentages will not be provided for a zero count and 100% will be provided to zero dps.

All output will be generated using SAS version 9.4 for safety analysis, and R software Version 4.3.1 or above for EBA analysis (including figures) and safety figures.

**Handling of Dropouts or Missing Data:** No missing data will be replaced, and it will be shown in any summaries as missing for all analyses.

**Treatment of Outliers:** TTP and CFU observations which are considered to be outliers by a team of microbiologist and clinical trialist, might be removed from the EBA analysis. Outliers and reason for removal will be documented.

If the start date of an Adverse Event (AE) (or concomitant medication) is incomplete, the most conservative approach will be taken and the AE treated as treatment emergent (or concomitant, in the case of medication) to the last study treatment given.

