## 10.2 Safety and Tolerability

### 10.2.1 Adverse Events

All adverse events will be coded using the Medical Dictionary for Regulatory Activities (MedDRA) and will be presented by Preferred Term within each MedDRA System Organ Class (SOC).

An adverse event will be defined as Treatment Emergent (TEAE) if the onset date is after the first intake of study medication.

Where dates are incomplete such that a decision cannot be made, it will be assumed that the adverse event is TEAE.

The incidence of the following events will be summarised by treatment group:

13. TEAEs by SOC and preferred term.
14. TEAEs by maximum severity.
15. TEAEs by strongest relationship to IP
16. Related TEAEs.
17. Potentially IMP-related (Related and Possibly Related) TEAEs.
18. Potentially IMP- TEAEs by maximum severity.
19. TEAEs with a fatal outcome.
20. Serious TEAEs.
21. Discontinuations due to TEAEs.

The frequency of TEAEs, by severity and IMP relationship, will be presented by treatment. The sampled and recorded observations of AEs will be considered to be discrete random variables. AEs will be analysed based on absolute risk or crude incidence rates or exposure-adjusted incidence rates using frequency statistics. The AE variable will be modelled as a Bernoulli distribution with parameter (p) representing the probability of success/occurrence. The definition of absolute risk applied in this analysis will be the following:

- The number of individuals experiencing an AE divided by the total number of participants in that dose treatment group.

Applicable only in the AE summary table14.3.1.8, the following definition of absolute risk will be used for this table:

- The number of AEs divided by the total number of AEs in that dose treatment group

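### No TEAE table separates the RESP301 treatment period from the HRZE that RESP301-alone completers start on Day 16

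*SAP*

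**What the plan says.** **Window.** SAP 5.2 gives the definition: "Treatment-emergent adverse events (TEAEs) are defined as AEs which started at or after the first administration of IMP". It adds events "which started prior to the first administration of IMP but which worsened after the first intake". The next sentence closes the window: events starting after "the first administration of IMP until the last scheduled visit/ assessment/ measurement will be regarded as treatment-emergent". Protocol 1.3, note F, matches this for collection: "Adverse Events: Collected from first dose of IMP to Follow-Up visit". The follow-up visit is on Day 28, ±3 days.

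**Second definition.** SAP 10.2.1 says: "An adverse event will be defined as Treatment Emergent (TEAE) if the onset date is after the first intake of study medication". It has no worsening clause and no end of window. It adds a default: "Where dates are incomplete such that a decision cannot be made, it will be assumed that the adverse event is TEAE". SAP 7 takes the same line: "If the start date of an Adverse Event (AE) (or concomitant medication) is incomplete, the most conservative approach will be taken".

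**Treatment sequence.** Protocol 5.1 gives RESP301 for 14 days. RESP301-containing arms are untreated on Day 15, and standard HRZE begins on Day 16. The HRZE-alone arm continues HRZE throughout.

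**Objective and outputs.** The secondary objective (SAP 3) is safety and tolerability over 14 days of treatment. SAP 11.2 lists Tables 14.3.1.1 to 14.3.1.8 for TEAEs. SAP 10.2.1 also plans a mean cumulative function, Kaplan-Meier and Cox analyses, and names exposure-adjusted rates. SAP 10.2.2 promises a summary of the stopping and amendment criteria by treatment group and time point, and the shell for Table 14.3.7 has a block covering all study days.

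**The concern.** In the three RESP301-alone arms the TEAE window covers two regimens in turn: RESP301, then a four-drug oral combination. The all-causality tables label both with the RESP301 arm. A reader of the tds, qd or bd column would take its incidence as the tolerability of RESP301, although part of it may have arisen on HRZE. With about 15 participants per arm, a few such events would visibly move a percentage, and dose schedules are to be compared on these columns.

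Two smaller matters go with this. The SAP holds two TEAE definitions that do not say the same thing. The interim criterion on grade 3 or higher AEs (SAP 9) does not say which arm and which period decide it.

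**Working it through.** The plan states no figure to reproduce, so the check is a comparison of texts plus day arithmetic.

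**1. Tables.** SAP 11.2 lists 14.3.1.1, .2, .3.1, .3.2, .4, .5, .6, .7.1, .7.2, .7.3, .7.4 and .8, which is 12 tables. They use the shells for 14.3.1.1, 14.3.1.2, 14.3.1.7.1, 14.3.1.7.4 and 14.3.1.8. Titles and shells break events down by arm, system organ class and preferred term, severity or relationship. Tables split by period: 0 of 12.

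**2. Participants.** RESP301-alone arms are tds, qd and bd: 3 × 15 = 45, and 45/75 = 60% of the planned total. The RESP301-plus-HRZE arm also takes HRZE from Day 16 but was already exposed to it, so it is outside this count.

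**3. Calendar time after the switch, for a completer.** Days from Day 16 to follow-up, divided by days from Day 1 to follow-up, assuming HRZE continues to that visit:

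| Follow-up on | Days on HRZE | Share of window |
|---|---|---|
| Day 25 | 25 − 15 = 10 | 10/25 = 40% |
| Day 28 | 28 − 15 = 13 | 13/28 = 46% |
| Day 31 | 31 − 15 = 16 | 16/31 = 52% |

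Scheduled AE visits tell a different story: 16 on Days 1-16 plus one at follow-up makes 17, of which 2 (Days 16 and 28) fall in the later period, or 2/17 = 12%. Neither share is a share of AEs.

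**4. Effect on an arm.** One participant of 15 whose only TEAE starts on HRZE adds 1/15 = 6.7 percentage points. As an illustration only, three would add 3/15 = 20.0 points. No document figure indicates how many to expect.

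**5. Can other planned outputs separate the periods?**
- Relationship tables: they report relationship to IMP, and SAP 2 names both RESP301 and HRZE as investigational products. The tables do not say which drug is meant, and they leave the all-causality tables unchanged.
- Mean cumulative function and Kaplan-Meier: these show timing, but no cut at HRZE start is specified.
- AE listing 16.2.6.1 and the planned analysis datasets: separation is possible from dates, but no such output is planned.

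**6. The two definitions.** They differ in three ways: at or after first IMP versus after it; worsening clause present versus absent; end of window stated versus not stated. The practical reach is small. AEs are collected only from first dose, and incomplete dates default to treatment-emergent. Pre-dose events enter mainly through serious AEs, where Protocol 7.2 says "SAE reporting begins from the time a participant enters screening through to the final visit".

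**7. Interim criterion.** SAP 9 allows at most 50% of participants with a grade 3 or higher AE. If the 15-person tds arm is the denominator (an assumption), 7/15 = 46.7% meets it and 8/15 = 53.3% does not. One participant whose only such AE began on HRZE could then decide the result. Counting later events can only make the criterion stricter.

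**The case against.** The strongest reply is that nothing here is an error. AEs are deliberately collected to follow-up, and a full-window TEAE table matches that rule. The phrase about 14 days in the objective can describe dosing duration. Kaplan-Meier applied to first TEAE and read at Day 15 would give the Days 1-15 incidence, and with analysis datasets a date filter is routine. The study tests no hypothesis and will list every AE. For the HRZE control, a Day 16 cut marks no change of treatment.

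Much of this stands. The full-window tables are legitimate and should stay, and separation does not depend on hand work. But the SAP fixes neither the event nor the reading day for Kaplan-Meier and specifies no cut, so the split would be chosen after results are seen. Showing the control arm in both periods gives a reference for the later one.

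Three stronger readings are tempting, and the documents do not support them:
- *About 46% of AEs are misattributed.* That figure is calendar time; the share of AEs cannot be estimated.
- *SAP 10.2.1 drops Day 1 events.* A Day 1 onset recorded without a time cannot be ordered against the dose, and the incomplete-date default would probably keep it. The eCRF is not in view, so a loss is not established.
- *The interim has no display by arm or time.* SAP 10.2.2 and Table 14.3.7 plan one. What is missing is the arm and period that decide. The Steering Committee Charter, also not in view, may settle this.

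**Conclusion.** The main point holds as a gap worth closing at low cost. As written, the all-causality TEAE tables place events that start on HRZE under the RESP301-alone arms, for 45 of 75 planned participants. Up to 46% of a completer's calendar window is involved (40% to 52% with the visit window) if all complete treatment and HRZE continues to follow-up. The effect on incidence is unknown beyond 6.7 points for each participant of 15 whose only TEAE starts in that period. The definition mismatch is minor and likely to touch few events. The interim point is secondary: a display is planned, but the SAP does not name the deciding arm and period.

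**What to change.** 1. Keep the full-window TEAE tables. Add the key ones split by onset date into Days 1-15 and Day 16 to follow-up, for all arms so that periods can be compared. Assign Day 16 onsets to the second period by rule, since the protocol's list of AE items gives an onset date and no time.
2. For early withdrawals, who are referred for standard TB treatment when they leave, cut at the recorded start of that treatment. Where it is unknown, use a date rule fixed in advance, such as the day after the last IMP dose, because some withdrawals have no follow-up visit.
3. Use one definition in SAP 5.2 and 10.2.1: onset on or after the date of first IMP, or worsening after it, with the same end of window.
4. At the interim, also report grade 3 or higher AEs for Days 1-15, and state in advance which arm and period decide the SAP 9 criterion.

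The cost is SAP wording and one extra table set, built from AE and concomitant-medication dates already collected. Trial conduct does not change. The downside is that late RESP301 effects appear in the second period, but they stay in the full-window total.

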### **5.3 Exploratory endpoints**

To explore the EBA variability due to potential M.tb sterilization in sputum samples as a result of nitric oxide (NO) contamination in sputum samples. [REDACTED]

[REDACTED]

[REDACTED]

[REDACTED]

[REDACTED]

[REDACTED]

[REDACTED]

## **6 Analysis Populations**

The Safety analysis population will consist of all randomised participants who took at least one dose of study treatment.

The EBA population will consist of all participants who have baseline and at least one post baseline TTP or CFU observation. There will be one EBA population for TTP and one for CFU.

## 7 General Principles

The SAP will be finalised and signed-off prior to database lock. Post-hoc analysis (analyses performed that are different from those described in the final version of the SAP) will be documented in the final CSR as changes to planned analysis. For the Demography, Safety and Tolerability, and EBA analyses, there will be two analysis periods, an interim analysis and an analysis at the end of stage 2 of the study.

All data collected will be listed, and sorted by treatment, participant number, visit, and time.

Descriptive summaries will be presented using summary statistics (e.g. number (n), mean, standard deviations (SD), median, first quartile (Q1), third quartile (Q3), minimum (min), maximum (max)) for continuous variables or number and percentage n (%) for categorical/discrete variables. Continuous variables will be expressed as median with interquartile range for skewed data and mean with SD for normal data. The percentages will not be provided for a zero count. The mean, median, SD, Q1, and Q3 will be presented to 1 more decimal place (dp) than the raw data, and min and max to the same number of dps as the raw data. Percentages will not be provided for a zero count and 100% will be provided to zero dps.

All output will be generated using SAS version 9.4 for safety analysis, and R software Version 4.3.1 or above for EBA analysis (including figures) and safety figures.

**Handling of Dropouts or Missing Data:** No missing data will be replaced, and it will be shown in any summaries as missing for all analyses.

**Treatment of Outliers:** TTP and CFU observations which are considered to be outliers by a team of microbiologist and clinical trialist, might be removed from the EBA analysis. Outliers and reason for removal will be documented.

If the start date of an Adverse Event (AE) (or concomitant medication) is incomplete, the most conservative approach will be taken and the AE treated as treatment emergent (or concomitant, in the case of medication) to the last study treatment given.

